**5) Background**

Seborrheic dermatitis is a common chronic inflammatory disorder with a prevalence estimated at 3-5% [1, 2]. Although the exact pathophysiology is unclear, seborrheic dermatitis is more prevalent in individuals that are more heavily colonized with the *Malassezia spp* fungal organism, those with more residual sebum (for example in neuropathic patients such as in Parkinson's disease), and in those with higher sebum production, which leads to more lipid byproduct build up [2]. Current topical treatments include the use of topical antifungals, topical steroids, and topical calcineurin inhibitors [3, 4]. The success of topical treatments requires long-term use and depends on the compliance of the patient. Furthermore, these treatments can expose patients to potential side effects such as atrophy, thinning of the skin and telangiectasias in response to topical steroids. Therefore, alternative therapies that provide long-term control are needed.

This pilot project investigates the use of PDT may be useful in the treatment of seborrheic dermatitis based on the following: 1) The *Malassezia spp* is capable of forming biofilms [5], 2) PDT has been shown to be effective against *Malassezia spp* [6, 7], 3) PDT can break up biofilms of both bacterial and fungal origin [8], and 4)

PROTOCOL TITLE: Pilot study for the use of photodynamic therapy in the treatment of seborrheic dermatitis

benzoyl peroxide, a prooxidant treatment similar to PDT, has been shown to be effective in the treatment of seborrheic dermatitis [9].

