### **14) Data Management**

This study will be a single blinded, randomized, intra-individual comparison study consisting of a total of 12 subjects. A power analysis is not truly applicable because this is a pilot study that utilizes a potential treatment for seborrheic dermatitis that has not been previously investigated. We plan to recruit up to 12 patients.

SASI-F scores and the SebuMeter® measurements will be compared within the treatment group and an intra-individual comparison will be performed by paired statistical testing such as the paired t-test. A p-value of 0.05 or less will be considered significant. All of the assessors will be blinded to the treatment groups. The primary endpoint will be complete clearance of the seborrheic dermatitis as an intra-individual comparison and statistically analyzed with a two-sided paired t-test. All participants will be included in the study on an intent-to-treat basis.

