### **15) Provisions to Monitor the Data to Ensure the Safety of Subjects**

PROTOCOL TITLE: Pilot study for the use of photodynamic therapy in the treatment of seborrheic dermatitis

The subjects will be monitored clinically during the treatment for any evidence of side effects such as pain or blisters. All of the treatments are done with topical ALA, which is an FDA approved drug.

No regular blood draws or labs will be necessary. No systemic effects are anticipated because all of the treatments are localized topical applications.

However, the patient will be given a contact number on the consent forms in case there are any treatment related adverse effects such as erythema, blisters, pain, or secondary infection. Any side effects will be noted in a secure document. Secondary infections will be treated with appropriate antibiotics and local inflammation will be treated with topical steroids as necessary.

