## **16) Withdrawal of Subjects**

Subjects may be withdrawn without their consent if they acquire any medical issues during the study period which require the use of any other topical medications, oral or parenteral steroids, oral or parenteral antibiotics. They may also be withdrawn if they are found to have any abnormal sensitivity/allergy to the ALA.

If a subject is to be withdrawn without their consent, they will be contacted and the reason(s) for their withdrawal will be explained in full. No further data will be collected from the subject.

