## **17) Risks to Subjects**

There is a low chance for any physical, psychological, social or legal injury from participation in the study. The patient will be warned of the standard risks of treatment with topical ALA including erythema, pain, blisters, increased temporary photosensitivity for 24 hours after treatments, and risk for hyper- and hypopigmentation.

These potential adverse events will be localized and can be adequately managed and controlled with wound care and topical antibiotics, if the subject were to develop a secondary infection at the treatment sites. It is also possible, although unlikely, that the subject may develop contact dermatitis after exposure to the topical ALA. This can be adequately managed with topical steroids and topical antibiotics, if necessary.

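### Section 14 promises intent to treat, but section 16 stops data collection at investigator withdrawal, so participants who react to ALA can lose later gradings by rule

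*Combined protocol and SAP*

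**What the plan says.** Section 14 (Data Management) sets the analysis: "The primary endpoint will be complete clearance of the seborrheic dermatitis as an intra-individual comparison and statistically analyzed with a two-sided paired t-test". It adds: "All participants will be included in the study on an intent-to-treat basis".

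Section 16 (Withdrawal of Subjects) gives two reasons for withdrawing a participant without consent. The first is a medical issue arising during the study that would "require the use of any other topical medications, oral or parenteral steroids, oral or parenteral antibiotics". The second concerns the study drug: "They may also be withdrawn if they are found to have any abnormal sensitivity/allergy to the ALA". Both are permissive. The paragraph on withdrawal without consent ends: "No further data will be collected from the subject".

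Two other sections bear on the triggers. Section 15, on side effects, says: "Secondary infections will be treated with appropriate antibiotics and local inflammation will be treated with topical steroids as necessary". Section 17 says: "The patient will be warned of the standard risks of treatment with topical ALA including erythema, pain, blisters".

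Section 11 schedules severity grading before each of two treatments and after each follow-up period. No section available to us says how a missing grading is counted, or keeps a withdrawn participant under observation.

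**The concern.** The two rules cannot both be followed. Section 14 needs a clearance result from every participant. Section 16 forbids collecting one after an investigator withdrawal. The participant in question has not refused further contact, so the loss is avoidable.

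The loss is also linked to the active treatment. One trigger is a reaction to ALA. The other can be reached from an ALA reaction, because section 15 manages local inflammation with topical steroids and secondary infection with antibiotics, and section 16 makes a need for other topical medication or antibiotics a ground for withdrawal. The pairs left for analysis then lean towards people who tolerated ALA, and an analysis of those pairs alone is not intent to treat.

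If such a participant is kept in the study, a related question arises. The later grading may follow a topical steroid, and section 5 names that class as a therapy for the disease: "Current topical treatments include the use of topical antifungals, topical steroids, and topical calcineurin inhibitors". The plan does not say how to handle such a grading.

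At stake is the size of the reported clearance difference, in a trial where each participant is one of 12 pairs.

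**Working it through.** The plan derives no figure that can be reproduced. It gives no power, effect size, standard deviation or withdrawal rate. The steps below measure how far lost gradings can move the result.

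**Inputs.** From section 14: 12 participants, two halves of the face each, a two-sided paired t-test on clearance, and significance at 0.05 or less. Assumed: the number withdrawn before the grading (k = 1, 2 or 3), the clearance counts, and the withdrawal risk w.

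**Step 1: the test.** Score each participant +1 if only the ALA half clears, -1 if only the control half clears, and 0 otherwise. With b scores of +1, c scores of -1 and n pairs, the difference is (b - c)/n and

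t = (b - c)·√(n - 1) / √[n(b + c) - (b - c)²], on n - 1 degrees of freedom.

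For b = 4, c = 0, n = 12: t = 4√11/√(48 - 16) = 2.345, p = 0.039. For b = 3, c = 0, n = 12: t = 3√11/√(36 - 9) = 1.915, p = 0.082. With no control-only clearances, 4 to 0 is therefore the smallest significant split, a difference of 4/12 = 33 points.

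**Step 2: uncertainty from each lost pair.** A lost score can be anything from -1 to +1. Relative to scoring it 0, k lost pairs can move the 12-participant difference by up to k/12 either way:

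- k = 1: 1/12 = 8.3 points
- k = 2: 2/12 = 16.7 points
- k = 3: 3/12 = 25 points

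**Step 3: bias if the withdrawn participants would have cleared on neither half.** Take 4 ALA-only and 0 control-only clearances among all 12, so the true difference is 33 points. Analysing only those still graded gives 4/(12 - k):

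| k | Reported difference | Factor 12/(12 - k) | p |
|---|---|---|---|
| 0 | 4/12 = 33 points | 1.00 | 0.039 |
| 1 | 4/11 = 36 points | 1.09 | 0.038 |
| 2 | 4/10 = 40 points | 1.20 | 0.037 |
| 3 | 4/9 = 44 points | 1.33 | 0.035 |

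**Step 4: does the decision change?** For every possible (b, c) split at n = 12, remove 1, 2 or 3 pairs that cleared on neither half and compare the decision at 0.05 before and after. It never changes. Under this assumption the bias affects the estimate and not the decision.

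**Step 5: how often.** The chance of at least one withdrawal among 12 is 1 - (1 - w)¹². For assumed w of 1%, 2%, 5%, 10% and 15% this is 11%, 22%, 46%, 72% and 86%. The documents do not say where in that range the trial lies.

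**The case against.** The strongest reply is that the practical harm is small.

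- **Both halves go together.** In a split-face design a withdrawal removes the whole pair, so the two treatments never lose different numbers. This stands. What remains is selection of pairs that tolerated ALA.
- **Withdrawal may be rare.** It is discretionary. Section 6 excludes known or suspected hypersensitivity, section 17 calls contact dermatitis unlikely, and the staff and resources text after section 23 expects no significant adverse effects. Erythema and blisters are standard risks in section 17, while section 16 requires an abnormal sensitivity. The medical-issue trigger can also be read as intercurrent illness, and section 15 can be read as on-study care without withdrawal. This stands as a limit on frequency. It does not remove the conflict when a withdrawal occurs.
- **Some gradings survive.** Section 16 does not discard gradings already taken. Section 14 does not name the grading used for clearance, and the flow diagram (Figure 2) is not shown. The point is therefore limited to gradings that fall after withdrawal.
- **It is a pilot.** That is so, but section 4 states an efficacy objective and section 14 sets a significance threshold and an intent-to-treat analysis.

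A reader might infer more than the documents support, in two ways.

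One is that a single withdrawal could move the trial across 0.05. Suppose a participant clears on the ALA half only at the first follow-up and is then withdrawn. Carrying that result forward can give 4 to 0 of 12 (p = 0.039), against 3 to 0 of 12 if counted as not cleared or 3 to 0 of 11 if excluded (p = 0.082 for both). Only carry-forward crosses the threshold, and the plan contains no carry-forward rule. An unseen grading could in principle matter, but that is true of any missing value among 12.

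The other is that any half treated with a topical steroid should count as not cleared. That is a debatable choice of estimand. It would fall mainly on the ALA half, where ALA reactions occur.

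**Conclusion.** The conflict between sections 14 and 16 is real and sits in the current text. A stated rule gives up gradings that the intent-to-treat analysis needs, for reasons that can follow from the active treatment.

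Its size is moderate: up to 8.3 points of uncertainty either way per lost pair, and a true 33-point difference reported as 36 to 44 points when 1 to 3 withdrawn participants are dropped. The second figure assumes that those participants would have cleared on neither half and that 4 of the 12 clear on the ALA half only. On that assumption the significance decision is unchanged. No inflation of the false-positive rate is claimed, and no withdrawal rate can be taken from the documents.

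The change is worth making because it prevents treatment-related missing data at almost no cost. The trial's conclusion has not been shown to depend on it.

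**What to change.** **Section 16.** Replace the stop on data collection with a stop on study treatment only. Continue the scheduled photographs and blinded SASI-F grading of withdrawn participants unless they refuse.

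**Section 14.** State that all randomised participants are analysed, that a half whose grading is still missing counts as not cleared, and that a completers-only analysis is reported as a sensitivity check.

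**Steroids and antibiotics.** Record any topical steroid or antibiotic use by side of the face and report a sensitivity analysis for it, without fixing those halves as not cleared.

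**Cost.** A few sentences of protocol wording, plus keeping already scheduled visits for participants who stop treatment. No additional participants or types of measurement are needed.

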### **15) Provisions to Monitor the Data to Ensure the Safety of Subjects**

PROTOCOL TITLE: Pilot study for the use of photodynamic therapy in the treatment of seborrheic dermatitis

The subjects will be monitored clinically during the treatment for any evidence of side effects such as pain or blisters. All of the treatments are done with topical ALA, which is an FDA approved drug.

No regular blood draws or labs will be necessary. No systemic effects are anticipated because all of the treatments are localized topical applications.

However, the patient will be given a contact number on the consent forms in case there are any treatment related adverse effects such as erythema, blisters, pain, or secondary infection. Any side effects will be noted in a secure document. Secondary infections will be treated with appropriate antibiotics and local inflammation will be treated with topical steroids as necessary.

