## **10) Study Timelines**

PROTOCOL TITLE: Pilot study for the use of photodynamic therapy in the treatment of seborrheic dermatitis

The research subject will require 4 visits that are spaced 2-10 weeks apart as outlined in the attached protocol. Each visit will take a total of 1.5 hours. We estimate that each subject will participate for a total of 3-4.5 months from initiation of enrollment to completion of the study.

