**Coordinators:**

- Role: Patient recruitment, blue light exposure, facial photography, grading of treatment site, specimen collection, data analysis

Seborrheic dermatitis is one of the most common conditions encountered in dermatology and among our patients. Therefore, we will have a sufficient recruitment pool to meet our required number of subjects.

Photodynamic therapy is frequently used at the Dermatology clinic and we do not expect significant adverse effects. However, the patient will be asked to contact the dermatology attending on-call in the event that there is an adverse effect.

To ensure that all assisting personnel are aware of the research protocols, we will have a pre-recruitment meeting followed by regularly scheduled meetings to discuss duty expectations, the protocol, study progress, and any changes as needed.

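### No adverse-event check is stated after the treatment session, so delayed local reactions may be under-counted and need not be recorded by side of face

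*Combined protocol and SAP*

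**What the plan says.** - **Monitoring.** Section 15 says "The subjects will be monitored clinically during the treatment for any evidence of side effects such as pain or blisters".
- **After the session.** The same section adds that "the patient will be given a contact number on the consent forms in case there are any treatment related adverse effects". The paragraph on resources under the coordinators' role says that "the patient will be asked to contact the dermatology attending on-call in the event that there is an adverse effect". Both routes start with the patient.
- **Recording.** "Any side effects will be noted in a secure document" (section 15). No schedule, grading, onset date or side of face is specified.
- **Named risks.** Section 17 lists erythema, pain and blisters, then "increased temporary photosensitivity for 24 hours after treatments, and risk for hyper- and hypopigmentation". It also foresees treatment "if the subject were to develop a secondary infection at the treatment sites", and says that "the subject may develop contact dermatitis after exposure to the topical ALA".
- **Visits.** Section 10 says "The research subject will require 4 visits that are spaced 2-10 weeks apart as outlined in the attached protocol. Each visit will take a total"; the planned length is 1.5 hours. Section 11 describes severity grading, swabs and sebum before each treatment and after each follow-up period. Section 12 adds photographs, taken for SASI-F grading.
- **Withdrawal.** Section 16 allows withdrawal without consent for sensitivity or allergy to ALA, or for a medical issue that needs other topical medication, or oral or parenteral steroids or antibiotics. It then stops all further data collection from that subject.

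**The concern.** The stated period of active monitoring does not match the risks the protocol itself names. The text places photosensitivity in the 24 hours after treatment and contact dermatitis after exposure. It gives no onset time for infection or pigment change, but late appearance is a reasonable inference. For all of these, the plan states no occasion on which staff ask about them or look for them.

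Three things are at stake.

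- **Under-counting.** A reaction that resolves between visits, and that the patient does not report, leaves no trace. A low count in a small pilot could then be read as good tolerability.
- **Loss of the within-person control.** One half of the face receives ALA and the other a placebo stick, and the face is then exposed to the light. Events recorded by side could be compared between halves. If the side is not recorded, that comparison may not be possible.
- **Missing outcomes where they matter most.** The subject withdrawn because of a reaction is the one whose data collection stops.

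**Working it through.** The documents give no safety calculation, so there is no figure to reproduce. The check is mainly a comparison of text, with some supporting arithmetic.

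**1. Named risk against stated detection**

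| Risk (sections 15 and 17) | Timing in the text | Stated detection |
|---|---|---|
| Pain, blisters | during treatment (section 15 examples) | clinical monitoring in the session; patient contact |
| Photosensitivity | 24 hours after treatment | patient contact |
| Contact dermatitis | after exposure to ALA | patient contact |
| Secondary infection | not given | patient contact |
| Hyper- or hypopigmentation | not given | patient contact |

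**2. Visit gap.** Section 10 gives 2 to 10 weeks, that is 2 × 7 = 14 days to 10 × 7 = 70 days. The 24-hour photosensitivity period therefore ends at least 14 − 1 = 13 days before the next visit. Anything learned about it then is recall.

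**3. What the follow-up visits measure.** SASI-F is (erythema + scale) × area fraction (section 12). It has no place for pigment change, infection or healed blisters. Erythema or scale from a reaction would be scored as disease. A persisting effect could still be seen by staff, but incidentally.

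**4. Withdrawal.** Sections 15 and 17 foresee antibiotics for secondary infection and topical steroids for local inflammation or contact dermatitis. Section 16 makes a need for other topical medication, or for oral or parenteral antibiotics, a possible ground for withdrawal. A treated reaction could thus lead to withdrawal and the end of data collection, as could ALA sensitivity itself. These sections must be reconciled as to data collection.

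**5. Illustration of under-capture.** Inputs: n = 12 (section 7); true risk p per subject and capture fraction c are assumptions, not in the documents. The probability of recording at least one event is 1 − (1 − pc)^12.

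| True risk p (assumed) | c = 1 | c = 0.5 | c = 0.25 |
|---|---|---|---|
| 5% | 1 − 0.95^12 = 46% | 1 − 0.975^12 = 26% | 1 − 0.9875^12 = 14% |
| 10% | 1 − 0.90^12 = 72% | 1 − 0.95^12 = 46% | 1 − 0.975^12 = 26% |
| 20% | 1 − 0.80^12 = 93% | 1 − 0.90^12 = 72% | 1 − 0.95^12 = 46% |

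With full capture, no events in 12 still leaves a one-sided 95% upper bound of 1 − 0.05^(1/12) = 22%. With incomplete capture the bound applies only to the recorded risk, and the true risk could be higher.

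**The case against.** The best case for the plan has four parts.

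- **Delayed harm is not captured only by telephone.** A reader might infer that it is. The documents do not support this: the instruction to note side effects is not limited to calls or to the session, and subjects return in person, are graded and are photographed. Persisting effects can be seen and noted. This stands. It does not close the gap, because an instruction to note what is learned is not an instruction to ask, and it does not help with effects that have resolved.
- **The face is examined before the second application.** A reader might infer that nobody is required to look. In fact section 11 requires severity grading before each treatment, erythema is part of the grade, and section 16 assumes that sensitivity can be found. This stands, but SASI-F grading is a disease score, and section 16 does not say how sensitivity would be found.
- **Some material cannot be seen.** Figure 2, the attached protocol cited in section 10 and the consent form are not available. An adverse-event check may be listed there. This cannot be excluded; if so, section 15 should state it.
- **Safety is not an endpoint.** No objective or endpoint concerns tolerability, and no side-by-side safety comparison is planned. The treated side is fixed and known to the investigator, so a recorded site would identify the arm. This limits the consequence. But nothing requires the site to be recorded, and the study will still report on a treatment it describes as not previously investigated in this disease.

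**Conclusion.** The concern holds in a limited form. In the text available, active monitoring is stated only for the treatment session, the only stated route for delayed effects is contact by the patient, and no solicited or side-specific check is stated for later visits. Persisting effects would be seen incidentally, and resolved ones could be missed. In addition, section 16 loses the outcome of a reaction that leads to withdrawal.

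The size cannot be estimated from the documents. The probabilities above (for example 93% falling to 72% or 46% at a true risk of 20%) show how under-capture works in 12 subjects. They rest on assumed risks and on a single capture rate for every type of event, and they are not a forecast for this trial.

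The conclusion assumes that the treatment in section 15 means the session, which is the likely reading although section 12 also uses the word for the whole split-face regimen. It also assumes that the unseen figure and attachment contain no check. It is a gap in ascertainment and recording that should be closed; it does not undermine the efficacy comparison.

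**What to change.** 1. **Amend section 15.** At each existing visit after a treatment, including before the second application and at the last visit, ask the blinded patient about the whole interval since treatment, and check each half-face for the risks in section 17. Record left or right, onset, severity and resolution.
2. **Protect the blinding.** Record without arm labels, preferably by someone other than the investigator who applies the ALA, since an assessor who knows the side could rate the halves differently. Keep the form apart from the blinded SASI-F photograph grading.
3. **Use one log.** Enter on-call contacts in the same record as events found at visits.
4. **Reconcile section 16 with section 15**, so that the outcome of an adverse event still open at withdrawal can be recorded, for example by telephone.
5. **Report descriptively.** After unmasking, tabulate events by ALA half and placebo half. Read erythema against the SASI-F grade, because it may reflect disease rather than harm.
6. **If Figure 2 or the attached protocol already contains a check**, state it in section 15.

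The cost is a wording change in two sections, a short form and a few minutes within each planned 1.5-hour visit, and an occasional call. More mild events will be reported. No additional visits are needed, and no dose, treatment or stopping rule is proposed.
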